13.1.11. Examination of Subgroups

The primary and secondary efficacy endpoints will be analyzed for subject subgroups based on the ITT population. Subgroups will be assessed at Baseline and only if there are a sufficient number of subjects in each group (eg, >5 subjects per group).

Baseline subgroups of interest are as follows: age, age at PBC diagnosis, sex, race, body mass index, ALP level, bilirubin level, use of UDCA, years since diagnosis of PBC, and geographic region.

The primary efficacy endpoint will also be assessed across the spectrum of PBC disease stage as defined by Rotterdam criteria ([Kuiper 2009](#))

- Early (normal albumin and normal bilirubin)
- Moderate (abnormal albumin or abnormal bilirubin)
- Advanced (abnormal albumin and abnormal bilirubin)

The primary efficacy endpoint will also be assessed for the following clinically relevant subpopulations.

- Monotherapy in patients who are intolerant or non-responsive to UDCA
- Elderly patients

Assuming a strong correlation between biochemistry and clinical outcomes using the total study population ([Section 13.1.5.1](#)) is observed, we will further assess the biochemical improvement in relevant subpopulations as applicable (eg, Rotterdam disease severity and monotherapy) and estimate the reduction in risk of clinical outcomes associated with the biochemical improvement.

Additional details regarding statistical methods and subgroup definitions will be provided in the SAP.

13.1.12. Continuous Monitoring and Interim Analyses

Blinded safety reports including the accrual of events, drop outs, and/or loss of subjects to commercially available OCA will be reviewed by the DMC on a regular basis.

Two planned interim analyses of the liver-related outcomes will be conducted using the Lan-DeMets O'Brien-Fleming boundaries ([Reboussin 2000](#)). Both interim analyses will be pre-specified and will occur after accrual of 50% (64 events) and 75% (96 events) of clinical outcome events, respectively.

The DMC will review the available efficacy data in conjunction with detailed safety data and other relevant information to recommend continuation, modification, or cessation (for efficacy)

of the study beyond each interim analysis. Modification of the study would not take place without prior agreement with regulatory authorities.

13.2. Safety Analysis

Safety data, including AEs and clinical laboratory observations, will be summarized by treatment group using the Safety Population.

13.2.1. Adverse Events

AEs will be coded using the Medical Dictionary of Regulatory Activities. Summary tables of treatment-emergent AEs will be provided. The incidence of TEAEs will be tabulated by system organ class and preferred term for each treatment group, and by severity and relationship to treatment. Tables of TEAEs leading to investigational product discontinuation and SAEs will be provided.

Adverse events of special interest as described in [Section 12.1.1.4](#) will be summarized for each treatment group. In addition, each event is a component of the primary endpoint, and will be summarized as secondary endpoints as described in [Section 13.1.4](#).

13.2.2. Clinical Laboratory Evaluations

Descriptive statistics summarizing central laboratory data (hematology and chemistry) will be presented for all study visits. Changes from pretreatment to each study visit will also be summarized by treatment group.

13.2.3. Additional Safety Analysis

Additional safety assessments include vital signs and ECGs. Descriptive statistics of the vital sign and ECG parameters will be presented by treatment group and study visit, as well as the change from pretreatment at each visit.

13.2.4. Cardiovascular Adjudication Committee

In addition to potential clinical endpoint events, cardiovascular events will be adjudicated. The adjudication of these events will be handled separately from the adjudication of events for assessment of the primary endpoint in this study. Adjudicated cardiovascular events include core MACE (cardiovascular death, nonfatal myocardial infarction, and nonfatal stroke) and expanded MACE (unstable angina requiring hospitalization, transient ischemic attack, peripheral or coronary revascularization procedures, hospitalization for congestive heart failure). Other events potentially related to adverse cardiovascular outcomes may be included in the Cardiovascular Adjudication Committee (CAC) Charter for adjudication. The adjudication of these events will be handled separately from the adjudication of events for assessment of the primary endpoint in this study (see [Section 13.4](#)).

13.3. Data Monitoring Committee

An independent DMC that includes hepatologists, pharmaceutical physicians, epidemiology/cardiology expert(s), and statistician(s) not involved in the study as Investigators, adjudication committee members, or consultants. The DMC will have oversight over the study

conduct as defined by the DMC charter. All members will have considerable experience with clinical study conduct and DMCs. Any candidate found to have a conflict of interest or whose name is listed on the FDA debarment list will not be offered membership. Conflicts of interest will be assessed regularly, and if members are found to have a new conflict of interest they will be replaced.

The DMC will meet approximately quarterly at scheduled meetings and ad hoc meetings will be convened, as appropriate, to review safety and efficacy data in order to ensure the safe and proper treatment of subjects. Based on review of these data, the DMC will advise the Sponsor on the validity and scientific merit of continuing the study.

Written minutes of both the open and closed DMC sessions will be prepared. The closed minutes will be made available to the appointed Sponsor representatives only after the database is locked.

Data listings provided to the DMC do not contain individual subject treatment information; however, the DMC will have access to the database and may unblind individual subject data as appropriate. Summary tables reviewed by the DMC during closed sessions will include an overall column containing information regarding all subjects and separate treatment columns with 'dummy' labels, ie, the actual treatment groups are used, but are not identified. Data reviewed during the meetings will include, at a minimum, disposition, demographics, exposure, clinical laboratory results, Medical Dictionary for Regulatory Activities (MedDRA) coded AEs, and AEs leading to early withdrawal of investigational product. At each meeting, detailed narratives of interval SAEs (including events resulting in death) are reviewed by the DMC in addition to a cumulative list of all SAEs.

The DMC may agree to adjust meeting frequency based upon actual and projected safety and efficacy data availability. Adjustments to or stopping of the protocol defined doses may be considered based on DMC evaluation of OCA safety and tolerability.

All Investigators and responsible IRBs/IECs will be informed of any decisions made by the Sponsor based on recommendations from the DMC relating to subject safety, which alter the conduct of this study. The Investigators will inform the subjects of such actions and the protocol, patient information sheet (PIS), and consent will be revised, as appropriate.

13.4. Adjudication Committees

All suspected liver-related clinical outcomes, and MACE/Expanded MACE, that occur after administration of the first dose of investigational product will be reviewed by the following blinded adjudication committees, depending on event type, before inclusion in any analysis. The 2 committees and event types they are responsible for adjudicating are as follows:

- Cardiovascular Adjudication Committee (CAC): Adjudicates all suspected MACE, including all deaths
- Hepatic Outcomes Committee: Adjudicates all deaths and suspected liver-related outcomes

Each adjudication committee will have a charter that documents the reporting of events by the study site, definition of the suspected events to be adjudicated, supply of source documentation

to the committee, entire data flow and process from committee membership, review of the events by the committee, reporting of the final assessment, and the working procedures of the committee.

The adjudication committee members will include experts with relevant adjudication experience; they will not be involved in the study as Investigators, DMC members, or consultants. Any candidate found to have a conflict or whose name is listed on the FDA debarment list is not offered membership. Conflicts of interest are assessed regularly, and if members are found to have a new conflict of interest they will be replaced.

The adjudication of suspected events will be based on available source documentation, including but not limited to individual clinical study data, hospital records, histology, discharge summaries, and/or death certificates. The adjudication committees will not receive any individual subject treatment or site-specific information. The assessment of events will be conducted in compliance with study-specific procedures, manuals, good clinical practice (GCP), and all other applicable regulatory requirements, including the archiving of essential documents.

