- Study 747-202 (165 subjects) evaluated 3 doses of OCA (10 mg, 25 mg, and 50 mg) versus placebo in subjects on a stable therapeutic dose of UDCA. Overall, the data from 747-202 were consistent with Study 747-201. Statistically significant and clinically meaningful relative and absolute reductions in ALP were achieved with all 3 doses of OCA versus placebo ($p < 0.0001$). Mean ALP reductions from baseline ranged from 21% to 25% compared to 3% with placebo. Improvements were also seen in GGT and ALT levels and in conjugated bilirubin levels.
- Study 747-301 (216 subjects) was a Phase 3, double-blind, placebo-controlled, parallel group study followed by an LTSE using OCA in subjects with PBC. The primary endpoint for Study 747-301 was a composite endpoint based on the

proportion of subjects reaching specific criteria for ALP and bilirubin (ALP $<1.67\times$ upper limit of normal [ULN] with a $\geq 15\%$ reduction and bilirubin \leq ULN). Both OCA treatment groups met the primary endpoint of achieving a reduction in ALP to $<1.67\times$ ULN with a $\geq 15\%$ reduction from baseline and a normal bilirubin level after 12 months of therapy. The placebo group experienced a mean decrease in ALP from baseline of 5%, compared to a significant mean decrease of 39% in the 10 mg OCA dose group and 33% in the OCA titration group (both OCA dose groups $p < 0.0001$ versus placebo).

The LTSE phases of both Phase 2 studies and the Phase 3 study support the long-term safety of OCA and demonstrate a durable therapeutic response. The LTSE phase of Study 747-301 is ongoing (a final CSR is pending); the LTSE phases of Study 747-201 and Study 747-202 are complete.

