7.3. Planned Dosing Regimen

Subjects will be randomized to treatment with either OCA or matching placebo in a 1:1 ratio. Subjects will be dosed according to their cirrhosis status (as defined [Section 7.5.4](#)) and applicable Child-Pugh Score (see [Section 7.5.5](#)) as outlined in [Section 7.4](#).

Table 3: Planned Dosing Regimen by Cirrhosis and Child Pugh Score

	Scheduled Dosing Regimen	
	Standard	Modified
	Noncirrhotic/ Child-Pugh A	Child-Pugh B or Child-Pugh C
Starting Dose ^a (Day 0)	5 mg daily	5 mg once weekly
Titration 1 ^b (≥Month 3)	10 mg daily	5 mg twice weekly ^c
Titration 2 ^b (≥6 weeks after Titration 1)	NA	10 mg twice weekly ^c

^a Starting dose based on subject's cirrhosis status and Child-Pugh score at Screening.

^b Planned titration regimen is shown; however, the titration of dose and/or frequency is dependent on subject tolerability, biochemical response, and/or changes in cirrhosis status or Child-Pugh score at any time during the study (see [Section 7.4](#)).

^c Dosing per the twice weekly schedule must be at least 3 days apart.

Non-Cirrhotic or Child-Pugh A

Subjects who are noncirrhotic or classified as Child-Pugh A at screening will receive 5 mg OCA or matching placebo once daily for 3 months. Subjects should titrate to a maximum dose of 10 mg OCA once daily (or matching placebo) at the Month 3 visit or at any study visit following the Month 3 visit based on tolerability of the product and assessment of biochemical response. Up-titration should be considered when ALP and/or total bilirubin are >ULN. A review of safety laboratory results (eg, chemistry, hematology, and coagulation) obtained no more than 2 months prior to the planned up-titration visit must be completed as part of the investigational product tolerability assessment before up-titration can occur (see [Section 7.4.1](#)).

For those subjects that up-titrate to 10 mg, dose may be decreased to 5 mg at any time during the study as considered clinically appropriate (eg, tolerability). Subjects may be titrated back up to a maximum dose of 10 mg once daily based on tolerability and clinical judgment of the Investigator. A review of safety laboratory results obtained within 2 months of the planned up-titration visit date is not required prior to re-challenging a subject up to 10 mg once daily dosing, as long as the decrease in dose/dosing frequency was less than 3 months in duration.

Cirrhotic and Child-Pugh B or C

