11.1.2.4. Potential Clinical Outcome Events

The events listed in [Section 12.1.6](#) will be initially assessed by the Investigator to determine if they are Potential Clinical Outcome Events. These events will be evaluated by an Adjudication Committee (described in [Section 13.4](#)) to confirm if they meet the criteria to be considered Clinical Outcome Events.

Given that the Potential Clinical Outcome Events could also meet the criteria of a suspected unexpected serious adverse reaction (SUSAR), which would necessitate unblinding for expedited reporting, the Sponsor will not expeditiously report suspected Potential Clinical Outcome events in order to retain the study blind and preserve the integrity of the clinical outcomes endpoint. These events will be selected as a “potential study event” on the Adverse Event eCRF and will be submitted for adjudication to the Adjudication Committee as described in [Section 13.4](#).

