13.1.2. Determination of Sample Size

The target population is subjects who are at higher risk of liver-related clinical complications. Eligible subjects will have a diagnosis of PBC with bilirubin levels $>ULN$ and $\leq 5x ULN$ and/or $ALP > 3 \times ULN$. The following assumptions were used in sample size calculations:

- Exponential survival curves, placebo survival estimate of 0.6 at 8 years with a hazard ratio of 0.60, and total study duration of 10 years (from first subject enrolled), allowing for 4 years of subject accrual and 6 years of follow up.
- Subjects will be randomized in a 1:1 ratio to placebo or OCA.
- The 2 groups will be compared using a 2-sided log rank test at the 5% level of significance.
- Two interim analyses and one final analysis are planned. The first interim analysis will be performed when 50% of the target events are accrued and the second interim will be performed when 75% of the target events are accrued.
- A dropout rate of 10% is assumed

Based on the randomization ratio, significance level, and assumed hazard ratio, a total of 127 events (both groups combined) will provide 80% power to demonstrate a statistically significant difference between OCA and placebo on time to liver-related outcomes, including all-cause mortality.

In addition, based on the remaining assumptions stated above, it is estimated that approximately 428 subjects will be enrolled to attain 127 events.

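### The Investigator, who follows ALP and so has a clue to the arm, makes the first call on which non-fatal hepatic events are potential primary events

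*Protocol*

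**What the plan says.** **Titration.** Section 7.3 says "Up-titration should be considered when ALP and/or total bilirubin are >ULN". Section 7.4 makes an inadequate fall in ALP and/or bilirubin a ground for up-titration. No section masks post-baseline ALP from sites.

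**ALP as a marker of OCA.** Section 5.4 reports for the Phase 3 study: "The placebo group experienced a mean decrease in ALP from baseline of 5%, compared to a significant mean decrease of 39" per cent in the 10 mg group, and 33% in the titration group. In the Phase 2 study on stable UDCA the falls were 21% to 25% against 3%. Section 5.5.2.1 says that most of the ALP effect is seen by 3 months, which is when titration can first occur.

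**Referral.** Under Section 11.1.2.4 the events listed in Section 12.1.6 "will be initially assessed by the Investigator to determine if they are Potential Clinical Outcome Events". Section 12.1.6 then has them flagged on the AE form and sent to the Hepatic Outcomes Committee.

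**Analysis.** Section 13.1.3 counts only adjudicated events. Section 13.1.9.1 makes an analysis of all events regardless of adjudication optional.

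**Committees.** Section 13.4 has all deaths and all suspected liver-related outcomes adjudicated, from sources "including but not limited to individual clinical study data, hospital records, histology, discharge summaries, and/or death certificates". It bars subject-level treatment and site information, and leaves event reporting, event definitions and document supply to a charter.

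**The concern.** The person who decides whether an event is put forward also follows the laboratory value that best distinguishes the arms. Blinded adjudication cannot repair this step, because an event that is never referred is never adjudicated and never counted.

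The exposed components are those that need clinical judgement and are not fatal: hospitalization for variceal bleed, for encephalopathy of West Haven grade 2 or more, or for spontaneous bacterial peritonitis, and uncontrolled ascites. The ascites component does not require hospitalization, so serious-event reporting does not necessarily catch it.

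If referral differed by arm, the primary hazard ratio would be biased, and so would the component analyses. A lesser matter is the dossier. Section 13.4 withholds treatment information but does not say whether dose history, OCA concentrations or pharmacodynamic laboratory values count as such.

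**Working it through.** **1. The plan's own figures.** Inputs from Section 13.1.2: "The 2 groups will be compared using a 2-sided log rank test at the 5% level of significance"; "Exponential survival curves, placebo survival estimate of 0.6 at 8 years with a hazard ratio of 0.60"; "allowing for 4 years of subject accrual and 6 years of follow up"; 1:1 allocation; 10% dropout; and the statement that "a total of 127 events (both groups combined) will provide 80% power".

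- Fixed design, Schoenfeld: 4(1.960 + 0.842)² / (ln 0.60)² = 120.3, so 121 events. Freedman: (1.960 + 0.842)² × (1.60/0.40)² = 125.6, so 126.
- With Lan-DeMets O'Brien-Fleming looks at 64, 96 and 127 events (bounds z = 2.949, 2.348, 2.016), power at 127 events is 81.3% (Schoenfeld drift) or 79.7% (Freedman drift).
- Hazards: −ln(0.6)/8 = 0.0639 on placebo and 0.0383 on OCA. Event probability is 1 − (e^(−6λ) − e^(−10λ))/(4λ) = 0.398 and 0.263, mean 0.331. Then 127/0.331 = 384, and 384/0.90 = 427, against 428 stated.

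The design figures reproduce, and this point does not change them.

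**2. How much ALP tells the Investigator.** Assume normal percentage changes with equal SD in both arms. The best single cut then guesses the arm correctly with probability Φ(d/(2·SD)), where d is the difference in mean change. The documents give no SD; 15 to 30 percentage points is an assumption. Guessing blind gives 50%.

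| Contrast (Section 5.4) | d | SD 15 | SD 20 | SD 25 | SD 30 |
|---|---|---|---|---|---|
| Phase 3, 10 mg: 39 − 5 | 34 | 87% | 80% | 75% | 72% |
| Phase 3, titration: 33 − 5 | 28 | 82% | 76% | 71% | 68% |
| Phase 2 on UDCA, high: 25 − 3 | 22 | 77% | 71% | 67% | 64% |
| Phase 2 on UDCA, low: 21 − 3 | 18 | 73% | 67% | 64% | 62% |

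The Phase 2 monotherapy study shows a wider contrast at 10 mg (44.5 + 0.4 = 44.9 points), giving 93% to 77%. It is the nearest reference for subjects not taking UDCA, whose share the protocol does not state.

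**3. What differential referral would do.** Let a share s of primary events depend on referral, with 90% referred on OCA and 95% on placebo. All three numbers are assumptions. The apparent hazard ratio is about the true one times (1 − s + 0.90s)/(1 − s + 0.95s).

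- s = 0.20: 0.98/0.99 = 0.990.
- s = 0.50: 0.95/0.975 = 0.974.

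A true ratio of 1.00 would read about 0.99 to 0.97, and 0.60 would read 0.594 to 0.585. With the bounds in step 1, one-sided type I error would move from 0.025 to between 0.028 and 0.035. With referral rates reversed, a null would read 1.01 to 1.03 and power at a true 0.60 would fall from 81.3% to between 79.8% and 77.2%.

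A heavier assumption, with 10% to 30% excess loss on OCA over the same shares, gives a null reading of 1 − 0.20 × 0.10 = 0.98 to 1 − 0.50 × 0.30 = 0.85, and type I error of 0.032 to 0.145. Nothing in the documents points to losses of that size. These sums also treat an unreferred event as lost for good. A subject who later dies, is transplanted or reaches MELD 15 would still count, only later, which softens the effect.

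**The case against.** The strongest reply is that several safeguards already stand. All deaths go to the committee. Transplant is a hard event, and MELD is calculated from laboratory values at all visits (Section 12.2.6). The hospitalized components are serious adverse events, and every such event must reach the sponsor with source records requested (Sections 12.1.1.2 and 12.1.5.2). Section 12.1.1.4 captures variceal bleeding, encephalopathy, ascites and peritonitis as events of special interest. The charter, which is not shown, may set referral rules and restrict dossiers. All of this stands, and it narrows the exposure. It does not close it: no section sends these records to adjudication without the Investigator's call, and Section 11.1.2.4 states that call as the rule.

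The titration decision itself is also a weak signal. A subject who enters at 3× ULN and responds at the Phase 3 mean still sits at 3 × 0.67 = 2.0 or 3 × 0.61 = 1.8 times ULN, and so remains a candidate for up-titration. The cue is the ALP value more than the dose step.

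A reader might go further and infer that ALP reveals the arm, or that adjudicators judge events knowing the treatment. The documents do not support either. ALP supports a better-than-chance guess. Section 13.4 bars treatment information, under which dose history and OCA concentrations can reasonably be read to fall. It neither names nor excludes ALP, and no section says who sees the trough OCA result of Section 7.7. Nor may one apply a referral difference to the whole composite, which would turn a null into 0.90/0.95 = 0.95: deaths, transplant and MELD are largely outside the filter.

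**Conclusion.** The point holds in a limited form. The protocol makes Investigator opinion the gate to adjudication for the judgement-dependent, non-fatal hepatic components, while giving that Investigator a partial clue to the arm. On the Phase 3 and on-UDCA contrasts the clue would support a correct guess about 62% to 87% of the time, under an assumed SD of 15 to 30 points.

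Neither the size nor the direction of any bias can be derived from the documents. With 20% to 50% of events filterable and 90% against 95% referral, a null hazard ratio would read about 0.97 to 0.99. That is an illustration, not an estimate. The case for change rests on the weak gate and the low cost of removing it. The question of dossier content is secondary and belongs partly to the charter.

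**What to change.** 1. **Section 11.1.2.4.** Replace the Investigator's first assessment with programmed referral. Every AE or SAE coded to the Section 12.1.6 terms, every Section 12.1.1.4 event of special interest, and every liver-related hospitalization or paracentesis record goes to the Hepatic Outcomes Committee regardless of Investigator opinion. Investigators may still add events.
2. **Section 13.1.9.1.** Change the sensitivity analysis of all events regardless of adjudication from *may* to *will*.
3. **Section 13.4 (secondary).** State that the barred treatment information includes dose and titration history and OCA concentrations. State also that post-baseline ALP, GGT, lipids, C4 and FGF-19 are left out of dossiers where the endpoint definitions do not need them. Bilirubin, INR and creatinine stay, for MELD.

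Sites would still see ALP; the change takes away the gate, not the cue. The cost is protocol and charter wording, a database query, some redaction work, and more referrals that end as non-events. Sample size and event target are unchanged.
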